Advanced Hybrid Closed Loop in Paediatric Population (HyCLIP)

CLINICAL TRIAL PROTOCOL

1 Trial Details			
Protocol/Clinical Trial Title:	Assessment of closed loop technology in young children with type 1 diabetes		
Protocol Number (Version and Date):	V9 07Nov2022		
Short Title:	Hybrid Closed Loop In Paediatric Population (HyCLIP)		
Trial Start Date:	August 2021	Trial Finish Date:	May 2023
Coordinating Principal Investigator Name:	[name]		
Coordinating Principal Investigator Contact Details:	[contact] [name]		
Sponsor Name (if applicable):	Telethon Kids Institute		

Trial Summary

There are an increasing number of young children diagnosed with Type 1 diabetes (T1D) and their management is challenging due to a combination of physiological factors and behavioural temperaments. This cohort is also adapting newer technological devices with parental supervision. However, the time in target range remains lower than in older children and adults. This increases the risk of immediate and long-term complications. There is strong evidence that glycaemic control in the first 10 years of life is a critical determinant of complication development in adulthood and therefore there is significant benefit from optimising glucose outcomes at this young age.

Automated insulin devices like hybrid closed loop (HCL) systems have been shown to reduce hyperglycaemia and improve glucose control in numerous trials and also in real world outcome data. They have provided a platform to improve time in range and glycaemic outcomes in older children and adults (Medtronic 670G approved for children above 7 years of age). Along with this, safety has been established. These systems remain to be tested in the young children with an algorithm which is more suitable for their needs. This study will explore the hypothesis that the advanced HCL (AHCL) system will reduce the glycaemic variability and thereby improve the glycaemic outcomes of children and improve the wellbeing of parents/caregivers.

This proposed study includes a 6-week feasibility phase followed by a 3-month multicentre randomised controlled study in children aged 2 to 7 years of age with T1D on insulin pump therapy. The participants will be randomly assigned to two groups: control group on standard therapy and the intervention group on AHCL system in the Medtronic 780G pumps.

The primary objective is to compare the proportion of *time in target range* (sensor glucose 3.9-10mmol/l) in young children with T1D while using AHCL or standard insulin pump therapy. The secondary aims are to determine the effect of AHCL on hypoglycaemia and hyperglycaemia and to determine the *psychological and social well-being* of caregivers compared to standard care.

The age of the participants means that this is placed in a category more than low risk although the level of parental supervision at this age and the use of a system that allows 24/7 glucose monitoring in reality more than mitigates this theoretical consideration. There are no potential ethical issues in the proposed study.

2 Rationale / Background

Background summary

The incidence of type 1 diabetes (T1D) is increasing by around 3% each year with a prevalence of 1 in 300(1) with most children diagnosed before adolescence. The management of T1D in young children places a combination of challenges to parents/caregivers and to health care professionals. Achieving glycaemic goals without increasing risk of hypoglycaemia remains the management strategy. However, the young age, unpredictable eating and activity patterns, small insulin doses and behaviour, and the organisation required place a significant burden on parents (2) which interfere with the ability to fine tune insulin delivery. The fear of nocturnal hypoglycaemia is common in parents of young children with T1D (3). This induces significant anxiety, poor sleep affecting the quality of life (4). This also leads to maladaptive behaviours permitting hyperglycaemia in an attempt to avoid hypoglycaemia with resultant impact on glycaemic management (5) which increases the risk of long-term microvascular and macrovascular complications. Time in range in this young cohort, not surprisingly, is less than in older children and adults with increasing evidence of reduced time in range associated with more microvascular complications (6). There is strong evidence that glycaemic control in the first 10 years of life is a critical determinant of development of complications in adulthood and therefore there is significant benefit from optimising glucose outcomes at this young age. This highlights the need for optimal management strategies to improve glycaemic outcomes and reduce the psychosocial stressors impacting the quality of life of both children and caregivers.

Technological advancements have provided a platform which could potentially enhance and improve the management of T1D without the risk of hypoglycaemia and glycaemic fluctuations. *Closed-Loop technology* integrates continuous measurement of interstitial glucose levels from a glucose sensor, a pump for delivering insulin and an algorithm that determines insulin delivery without patient intervention. It offers the potential to circumvent the significant glycaemic excursions associated with conventional therapy. AHCL has an automated insulin delivery based on sensor glucose feedback system (AutoMode) although it still requires the user to administer mealtime bolus insulin.

This device was first tested for use in patients >14 years old. AHCL therapy was safe during in-home use by adolescents and adults with increased time in target, and reductions in HbA1c, hyperglycaemia and hypoglycaemia, compared to baseline (7). This system is currently approved for children above 7 years of age after a safety evaluation for 3 months in children between 7-13 years of age (8). The recognition of improved safety of these devices have led clinicians to use these closed loop systems in young children as an off-label use. There have been safety and efficacy reports of children using the 670G AutoMode in a retrospective analysis in 16 children < 7 years of age (mean 4.3±1.2 years, range 2-6) *after off-label use* of the system in a tertiary paediatric diabetes centre (Seattle Children's Hospital) with a follow-up period of three to 12 months (mean 6.3 months) (9). These children were required to have a minimum of 8 units of insulin a day to qualify for Auto Mode use as per the design of the system. The case series showed the glycaemic control improved with no serious adverse events. This shows an unmet need to test these algorithms in clinical trials which will help in optimising diabetes management in this age group. This also highlights the confidence in clinicians to trial these devices in younger age group than standard insulin pump therapy (open loop systems) which have no control over insulin delivery in real-time.

The algorithm in the commercially available Medtronic 670G pump has been modified to increase time in range with automated correction boluses and additional target set point in order to reduce AutoMode exits and improve user experience and the time spent in AutoMode. Results of the in-home USA pivotal trial in 118 adults and 39 adolescents aged 14-75 years old with this AHCL algorithm showed that the trial successfully met both safety and glycaemic endpoints and demonstrated no occurrences of severe adverse events (10). Likewise, the device was also studied in a cross-over study in 60 individuals with T1D aged 7-70 years and reported significant improvement in glycaemic control with improvement in time in target by 12.5% with no increase in hypoglycaemia (11). These short-term studies with 4 to 6 week of AHCL use have provided the preliminary safety data in children and adults.

This algorithm is also being currently tested in the ongoing multicentre randomised controlled trial (RCT) in adolescents and young adults with suboptimal glycaemic control (RGS0000000886). Algorithms have also been studied in the younger population (1-7 years) and these studies have established preliminary feasibility and safety with use of the systems in short term(12, 13).

The study device used in this project (MiniMed 780G Pump) has a CE mark (Europe) however; it does not at this point in time have TGA or FDA approval and hence is an investigational device. The MiniMed 780G Pump is similar to the existing Medtronic 670G insulin pump, with the exception that it has an advanced algorithm as above (10,11) and has an added feature of Bluetooth connectivity which permits remote monitoring. The study proposes to conduct a two-phase study. The first step is to conduct a feasibility phase to establish the clinical parameters and settings of the device to inform the second phase of a longer RCT to test for the effectiveness of the device in this age group.

This proposal explores the hypothesis that this AHCL system will result in improved glycaemic control in young children compared to standard therapy. The study will examine the glycaemic outcomes, but have a strong emphasis on anxiety and quality of life in the caregivers.

Intervention

The **advanced hybrid closed loop system** comprises the Medtronic MiniMed™ 780G insulin pump containing the AHCL algorithm, and communicates via bluetooth wireless communication with the compatible devices in the MiniMed 780G System. The MiniMed 780G Pump works with the following major components: 1) Continuous Glucose Monitoring (CGM) that includes the Guardian Link (3) Transmitter that is connected to the Guardian Sensor (3) to receive sensor glucose values at 5 minute intervals; 2) blood glucose meter (Roche Accu-Chek®) that will be used to calibrate the sensor and has the ability to send blood glucose values wirelessly as a convenience to the user; 3) MiniMed Mobile App to allow upload of data wirelessly to the CareLink therapy management software; and 4) Pump Accessory devices to deliver insulin (infusion sets and reservoirs)..

The algorithm is contained in the pump and receives sensor glucose data every 5 minutes, computing and adjusting “basal rate” insulin delivery based on the glucose levels. Therefore, standard “basal” insulin that is pre-programmed in standard insulin pump therapy is replaced by the algorithm-derived insulin delivery (given as a micro-bolus every 5 minutes). Automated correction doses will be delivered by the system as per the set target glucose levels. Meals will still be announced, and an insulin bolus delivered according to the individualised patient’s carbohydrate ratio.

Unlike the HCL available in the commercially available Medtronic MiniMed™ 670G,

- 1) This system is designed to automate the delivery of correction boluses when the user experiences, or is predicted to experience, prolonged high glucose levels based on their sensor glucose readings.
- 2) The system has additional target points (5.5 mmol/L, 6.1 mmol/L, and 6.7 mmol/L),
- 3) The system will also have an additional Bluetooth capability which will make it possible to monitor the glucose level via a phone app and is therefore more suitable for this young cohort.

Glucose monitoring: All participants will be issued with a study meter (Roche Accu-Chek®) and test strips will be provided. For participants randomised to AHCL, this allows for data to be directly sent to the insulin pump.

CareLink Software: The Carelink Therapy Management System (CareLink) is a Medtronic web-based platform which is used for storing insulin pump data. Insulin pump data is then accessible for download by the investigators.

3 Trial Aims / Objectives / Hypotheses

Aims:

Feasibility phase

The primary aim of the 6-week feasibility phase is to increase the clinical experience with the device and to identify logistical barriers that may affect the optimal conduct of the subsequent randomised controlled trial (RCT).

Secondary aims of the feasibility phase are:

1. To assess the likelihood of uptake and engagement with the device (MiniMed 780G Pump)
2. To gather further estimates of glycaemic control metrics in children with T1D

Randomised Controlled Trial (RCT) phase

The primary aim of this phase is to determine the effectiveness of 3 months AHCL versus standard therapy (CSII with or without CGM) on time in target glucose range (3.9-10.0 mmol/L) in young children with type 1 diabetes.

The secondary aims are

1. To determine the effect of AHCL on *psychological and social well-being* of caregivers compared to standard care.
2. To determine the effect of AHCL on *glycaemic parameters (on hypoglycaemia and hyperglycaemia)* compared to standard care.
3. To explore the relationship between dietary intake and the use of AHCL compared to standard therapy.
4. To determine the cost effectiveness of AHCL compared to standard therapy with regard to parental quality of life.
5. To determine the user interactions with the device (human factors) to understand strategies to improve outcomes.

Hypotheses

1. AHCL will improve time in range as compared to standard insulin pump therapy
2. AHCL will have a positive impact on quality of life and fear of hypoglycaemia (as determined by parent questionnaires) compared to standard insulin pump therapy.
3. AHCL will be a cost-effective intervention for the management of type 1 diabetes compared to standard insulin pump therapy.

4 Trial Design

4.1 Study Endpoints

Feasibility phase

- a. A collated list of difficulties/solutions encountered in this phase
- b. Recruitment rate
- c. Retention rate
- d. Device setting adjustments
 - i. Insulin carbohydrate ratio
 - ii. Active insulin time
- e. Glycaemic control
 - i. HbA1c (%)
 - ii. Percent time in range (3.9-10 mmol/L)
 - iii. Coefficient of variation of sensor glucose values

RCT Phase

The glycaemic endpoints chosen for the study are as provided by the consensus report for artificial pancreas trials (10). The psychological well-being of parents will be assessed using validated questionnaires.

Primary endpoint: Time in range (3.9-10 mmol/l) collected at baseline and at study end (3 months)

Secondary endpoints:

1. Psychosocial well-being (parents)
 - a) Functional health status QOL: WHO 5, EQ5D
 - b) Fear of hypoglycaemia: HFS Parent
 - c) Diabetes-related distress: PAID-Parent
 - d) Anxiety: GAD-7
 - e) Sleep quality: Pittsburgh Sleep Quality Index
 - f) Technology acceptance and satisfaction: DTQ
 - g) Semi structure interview
2. Glycaemic outcomes:
 - a) HbA1c
 - b) % CGM Time <2.8 mmol/L
 - c) % CGM Time <3.0 mmol/L
 - d) % CGM Time <3.3 mmol/L
 - e) % CGM Time <3.9 mmol/L
 - f) % CGM Time 3.9-7.8 mmol/L
 - g) % CGM Time >10.0 mmol/L
 - h) % CGM Time >13.9 mmol/L
 - i) % CGM Time >16.7 mmol/L
 - j) Glycaemic variability: Standard Deviation and Coefficient of Variation of CGM values
3. Nutritional adequacy of child's diet
24- hour food recall to identify the proportion of children meeting current macronutrient ratios (for fat, protein and carbohydrate expressed as % of total energy intake) as per International Society for Pediatric and Adolescent Diabetes (ISPAD) Nutrition Guidelines on any given day, and food group serves as per the NHMRC's Australian Guide to Healthy Eating for Children and Adolescents recommendations.
4. Health-economic outcomes:
 - a) QALYs calculated from the EQ-5D
 - b) Hypoglycaemic events and HbA1c
 - c) Admission to hospital due to diabetes-related events
 - d) Parental work interruption and leave due to child's diabetes
 - e) Child's school absenteeism due to diabetes
 - f) Investigator reporting time spent on training, education and support, by the type of health professional resource used
 - g) Diabetes management consumables (glucose strips, ketone strips, batteries, sensors, site dressings, lancets, needles, insulin)
5. Human factors:
Determine the participant technology interaction and adherence patterns with the use of AHCL.

Study Device Overview

The MiniMed 780G is an ambulatory, battery operated, rate-programmable micro infusion pump. It is intended for continuous delivery of insulin for the management of diabetes in persons requiring insulin.

In addition to insulin delivery, the pump is designed to receive, display, and store real-time sensor glucose values from a compatible glucose sensor transmitting device that is part of a continuous glucose monitoring system. The sensor signals are converted by the transmitter to sensor glucose values (based on calibration values from a blood glucose meter) which are then transmitted wirelessly to the pump for display to the user.

When used with CGM, sensor signals are converted by a compatible transmitter to sensor glucose values (based on calibration values from a blood glucose meter) which are transmitted to the pump for display to the user. Sensor glucose and insulin delivery data is stored by the pump and may be further uploaded to a personal computer using a Medtronic therapy management software application via a compatible communication device. Uploaded data can be used to track patterns and improve diabetes management. The MiniMed 780G Pump leverages existing pump therapy and allows the user to optionally use an off-the-shelf suitable consumer electronic device to more conveniently assist with the management of their therapy. The MiniMed 780G Pump is similar to an existing Medtronic insulin pump, the MiniMed 670G Pump (CE Marked), with the exception that it is Bluetooth enabled and contains modifications to the closed loop Algorithm. The modifications to the closed loop algorithm include the addition of adjustable target setpoints (5.5mmol/L, 6.1 mmol/L, and 6.7 mmol/L), an auto correction bolus without user input or acknowledgement and fine tuning of safeguards in order to reduce auto mode exits and improve user experience.

The MiniMed 780G System has the capability to operate in Manual Mode (also referred to as open loop) or SmartGuard (also referred to as Advanced Hybrid Closed Loop (AHCL), Auto mode or closed loop).

- Manual Mode is when insulin delivery is the responsibility of the user and will be based on the user defined basal rates. Meal boluses are the responsibility of the user. Manual Mode also has the capability of suspending insulin if the sensor glucose is predicted to fall below predefined threshold values (also referred to as Suspend on Low/Suspend Before Low)
- SmartGuard is when the insulin delivery is being commanded by the AHCL algorithm to a set threshold of 5.5 mmol/L, 6.1 mmol/L, and 6.7 mmol/L as determined by the user. The AHCL algorithm will calculate the insulin dose at five-minute intervals, based on CGM data, in order to achieve glycaemic control throughout the day. Meal boluses are the responsibility of the user.

Advanced Hybrid Closed Loop Algorithm (SmartGuard)

SmartGuard (also referred to as AHCL) is part of the Smart Guard technology that is an optional feature. When SmartGuard is on, the AHCL algorithm will calculate the insulin dose at 5-minute intervals, based on CGM data, to the set threshold of either 5.5 mmol/L, 6.1 mmol/L, or 6.7 mmol/L as determined by the user. Users have the option to enable automatic delivery of correction boluses.

The MiniMed 780G Pump works with the following major components: 1) Continuous Glucose Monitoring (CGM) that includes the Guardian Link (3) Transmitter that is connected to the Guardian Sensor (3) to receive sensor glucose values at 5 minute intervals; 2) blood glucose meter that will be used to calibrate the sensor and has the ability to send blood glucose values wirelessly as a convenience to the user; 3) MiniMed Mobile App to allow upload of data wirelessly to the CareLink therapy management software; and 4) Pump Accessory devices to deliver insulin (infusion sets and reservoirs).

The pump interfaces with devices within the MiniMed 780G System to provide therapy to patients.

MiniMed 780G Pump (MMT-1885)

The MiniMed 780G Insulin Pump houses electronics, a pumping mechanism, a user interface, and a medication reservoir within the same physical device. The insulin pump communicates via BLE wireless communication protocol with the compatible devices in the MiniMed 780G System: Transmitter, Roche's Accu-Chek Guide™ Link Blood Glucose Meter, consumer electronic devices with the MiniMed Mobile App, and Blue Adapter with CareLink.

MiniMed 780G pump is an insulin delivery system designed to help people living with diabetes and on intensive insulin pump therapy. MiniMed 780G is the next iteration in Medtronic's hybrid closed loop technology for closed loop insulin delivery. In addition to delivery of insulin, the MiniMed 780G pump is designed to receive and display real-time glucose values received via a compatible transmitting device (as applicable). Glucose values and pump history can be stored for later upload so that it can be analyzed to track patterns and improve diabetes management via the Carelink Therapy Management System.

Glucose Sensor Transmitter – Guardian Link (3) Transmitter (MMT-7911)

The glucose sensor transmitter is a component of Medtronic Diabetes CGM. The Guardian Link (3) Transmitter is a portable, electrical current meter intended to process, store, and transmit glucose sensor values to the compatible insulin pump. The Guardian Link (3) Transmitter sends sensor glucose (SG) values and sensor integrity (SI) data from the Guardian Sensor (3) to the compatible insulin pumps via BLE wireless communication protocol.

Glucose Sensor – Guardian Sensor (3) [MMT-7020]

The Guardian Sensor 3 is used with Medtronic Diabetes glucose sensing systems to continuously monitor glucose levels in persons with diabetes. The existing sensor is compatible with the MiniMed 780G System with no design changes necessary.

BG Meter

The Roche Accu-Chek® Guide Link Blood Glucose Monitoring System (BGMS) is the BG meter that is compatible with the MiniMed 780G pump and indicated to send BG readings wirelessly to the pump via BLE communication. The BG meter can also be used without being linked to the pump with BG values being entered manually via the pump user interface.

Accessories

Carelink Therapy Management System (Personal-MMT-7333, System-MMT-7350,)

The Carelink Therapy Management System is an optional accessory device that tracks patterns and is used to improve diabetes management. The Carelink software supports data uploads from the MiniMed 780G pump to the cloud through the Mobile App or PC/Mac application using a Blue Adapter. Additionally, Carelink Connect is a set of features that allows for display of CGM and pump data on compatible consumer electronic devices for a CarePartner. For uploading to Carelink, the patient uses either the MiniMed Mobile App or the Blue Adapter.

MiniMed Mobile App/CareLink Connect App

The MiniMed Mobile App is an optional accessory that is not a medical device which receives pump data via BLE communication. The MiniMed Mobile App provides users with the convenience to transfer pump data to CareLink and also provides a mirroring display of the pump screen. The MiniMed Mobile App is not designed to control or monitor the performance of the insulin pump nor for direct monitoring of pump data. As a mirroring display, the app can provide alerts to the patient via the user interface. All alerts must be addressed on the insulin pump.

The MiniMed Mobile App will then interface with the **CareLink Connect App** that is an optional accessory that is not a medical device which receives pump data wirelessly from the CareLink server. The **CareLink Connect App** provides a mirroring display of the MiniMed Mobile App screen, for remote monitoring by a care partner (i.e. care giver or health care provider). The **CareLink Connect App** is not designed to monitor the performance of the insulin pump nor for direct monitoring of pump data. As a mirroring display, the app can provide notifications to the care partner via the user interface.

Blue Adapter

The Blue Adapter (also known as the BLE Dongle) is a USB accessory that allows for data uploads from MiniMed 780G pump to Carelink via USB interface of PC or Mac devices. The Blue Adapter is a commercial-off-shelf-component provided by Career Technologies. The Medtronic accessory number is ACC-1003911. The Blue Adapter is not a medical device thus no labeling is needed

Reservoir and a Tubed infusion set

Besides BLE communication with system components, the pump system employs a reservoir and a tubed infusion set to create an insulin delivery pathway. The pump is durable devices while the reservoir and infusion set(s) are single-use consumables that are replaced at regular intervals. The pump and reservoir can connect to a range of infusion sets to accommodate different users and different use conditions.

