Visit 4D: Review of AHCL (after 4 weeks from commencement of AHCL, 1 hour)

Face-to-face meeting to upload insulin pump, review CareLink reports and revise settings (CHO ratio and Insulin action time)

Participants will be issued with enough consumables for the study.

Research staff will review CGM data at 8 weeks' with participants encouraged to contact the team if support/assistance required.

VISIT 5 (11 weeks after randomisation for control arm only)

Visit 5A: Insertion of blinded CGM: This constitutes first of the two sensors, each sensor provides data for 7 days. Parents will be instructed to test their children for a minimum 3 to 4x/day using the study meter.

Visit 5B: Insertion of 2nd blinded CGM: Participants will return 7 days after sensor insertion to remove and download the first week of CGM data. The study meter will be uploaded. A new sensor will be inserted and a fresh transmitter attached.

A total of 2 weeks of blinded sensor is required with at least 10 days of data. In participants who do not meet this requirement, repeat sensors will be offered till a maximum of 4 attempts of data collection

Visit 5C: Insertion of 3rd blinded sensor (if applicable)

Visit 5D Insertion of 4th blinded sensor (if applicable)

VISIT 6 (1 week after last blinded sensor) **End of RCT Phase**

The following data will be collected:

1. Auxological
 - a. Height
 - b. Weight
 - c. BMI
2. Diabetes clinical
 - a. HbA1c
 - b. Total daily dose of insulin (mean of previous 7 days)
 - c. Pump upload (for intervention group)
 - d. Severe hypoglycaemia since Visit 5 for Control arm / Visit 4d for Intervention arm
 - e. Diabetic ketoacidosis since Visit 5 for Control arm / Visit 4d for Intervention arm
 - f. Hospital admissions since Visit 5 for Control arm / Visit 4d for Intervention arm
3. Psychology measures: Psychological scales will be administered to parents on an electronic platform.
 - a. Functional health status: Quality of life (QOL) WHO 5, EQ5D
 - b. Fear of hypoglycaemia: Hypoglycaemia fear survey Parent
 - c. Diabetes-related distress: Problem Areas in Diabetes PAID-Parent version
 - d. Anxiety: GAD-7
 - e. Sleep quality: Pittsburgh Sleep Quality Index
 - f. Technology acceptance and satisfaction: DTQ
4. 24-hour food recall interview (to capture dietary pattern)
5. Parents of participants will be offered a semi-structured interview at the end of the study to share the lived experiences with use of new technology.

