4.9 Trial Termination

Study participation is voluntary, and participants may withdraw at any time. The DSMB will report to the ethics committees and investigators if stopping the study is required.

In general, once a participant is randomised, he/she will remain in the study unless the investigator believes it is not safe for the participant to continue. However, the criteria below will be used to determine whether use of the AHCL should be discontinued for a participant.

1. Severe hypoglycaemia (seizure or coma or any episodes requiring glucagon).
2. Severe diabetic ketoacidosis (venous ph <7.2)
3. Non-compliance with the protocol or development of a new medical condition or need for chronic use of a medication which in the judgment of the investigator increases risk for the participant

If AHCL use is stopped according to the above criteria, but the participant is willing, they will remain in the study and will continue to make all of the scheduled visits and participate in all monitoring.

The primary analysis will be intention to treat. Since participants in the usual care arm are following their normal diabetes care regimen, there will be no change in their participation in the study if they experience one of the events that would trigger stopping.

Criteria for Suspending/Stopping Overall Study

The DSMB will provide guidance to the Lead Investigator as to whether the overall study should be stopped.

In case of a recurring system malfunction or participant safety issue observed with multiple participants, the overall study will be suspended while the problem is diagnosed. The study may resume if the underlying problem can be corrected by a protocol or system modification that will not invalidate the results obtained prior to suspension.

The primary safety outcome will be

Severe hypoglycaemia (coma, convulsion or any episodes requiring glucagon). A sequential monitoring approach described by Kramar and Bascoul-Mollevi (2009) will be taken to determine study cessation rules due to excess severe hypoglycaemia. As hypoglycaemia events are experienced during the study, the DSMB will be notified in real time. The maximum acceptable rate of severe hypoglycaemia as well as the approach taken with regard to 'alpha spend' to preserve the nominal alpha of 0.05 will be determined in conjunction with the DSMB prior to the commencement of the study.

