Continuous secondary outcomes (glycaemic, auxological, clinical, psychosocial) will be analysed using the ANCOVA approach described above. The same assessment of model residuals will be conducted, and the appropriate analysis approach utilised. Where parametric methods are employed using the untransformed outcome measure, mean difference with 95% CI will be presented; where data are transformed, the retransformed effect with 95% confidence intervals will be presented as an indication of the relative effect of the intervention; where non-parametric methods are employed, Hodges-Lehmann median difference with robust 95% CI will be presented.

Secondary count outcomes will be analysed using Poisson regression or, where overdispersion is apparent, negative binomial model with a maximum likelihood-estimated dispersion parameter. 'Exposure' will be the number of hours wearing the sensor for CGM-derived outcomes and total number of days enrolled in the study for non-CGM-derived outcomes.

To assess the cost effectiveness of the intervention, the 'cost per quality of life year (QALY)' will be calculated using an incremental cost effectiveness ratio.

All hypothesis testing will be two-sided with an α of 0.05. No corrections for multiplicity are planned to control Type I error; rather, the effectiveness of the intervention will be assessed based on the clearly specified primary outcome; secondary outcomes are exploratory in nature and will be labelled as such in publications arising from the study.

No interim analyses are planned apart from the DSMB safety review reported above.

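### Diabetes-related admissions are assigned to Poisson or negative binomial regression, which gives no usable rate ratio if an arm has no admissions, a likely result with about 8 to 9 child-years per arm

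*Protocol*

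**What the plan says.** Section 4.1 (RCT Phase, health-economic outcomes) lists "Admission to hospital due to diabetes-related events" as secondary endpoint 4(c). Section 9.1 fixes one method for every outcome of this type: "Secondary count outcomes will be analysed using Poisson regression or, where overdispersion is apparent, negative binomial model with a maximum likelihood-estimated dispersion parameter". The exposure is sensor-wear hours for CGM-derived counts and "total number of days enrolled in the study for non-CGM-derived outcomes".

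Section 9.1 gives continuous outcomes several fallbacks: transformation, a rank test and the bootstrap. The only fallback for counts is the negative binomial model. No admission rate, expected number of events or precision is stated. Section 9.1 also says that secondary outcomes are exploratory and that effectiveness is judged on the primary outcome.

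**The concern.** Poisson and negative binomial regression estimate the treatment effect as a log rate ratio by maximum likelihood. If one arm has no events, that estimate runs off to plus or minus infinity and its standard error grows without limit. If neither arm has events, the ratio is undefined. The negative binomial model handles extra variation between children and does nothing for an empty arm.

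With about 35 children per arm followed for three months, an empty arm is an ordinary possibility for admissions. The specified analysis would then return no usable estimate or interval, and the p value would depend on whether the software reports a Wald or a likelihood-ratio test, which the protocol does not say. It would also give no upper bound on the rate in an arm without events, which is the informative number in that case.

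**Working it through.** **Inputs from the protocol.** 31 children per group required, 70 recruited in two equal groups (9.2); three months per child (4.8); two-sided alpha 0.05 (9.3).

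**The plan's own figure.** The only design figure is the primary-endpoint sample size. The normal-approximation formula gives 2 × (1.96 + 0.84)² × 11.5² / 8² ≈ 32.4, so 33 per group against the 31 stated; power at 31 is about 78%. That is close enough and does not affect this point. There is no figure for count outcomes to reproduce.

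**Exposure.** 31 × 0.25 = 7.75 and 35 × 0.25 = 8.75 child-years per arm.

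**Chance of an empty arm.** No rate is stated, so 5, 10 and 20 admissions per 100 child-years are assumed, equal in both arms. With m = rate × child-years, P(a given arm empty) = exp(−m), P(at least one empty) = 1 − (1 − exp(−m))², and P(both empty) = exp(−2m).

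| Assumed rate per 100 child-years | Expected per arm | Given arm empty | At least one empty | Both empty |
|---|---|---|---|---|
| 5 | 0.39–0.44 | 65–68% | 87–90% | 42–46% |
| 10 | 0.78–0.88 | 42–46% | 66–71% | 17–21% |
| 20 | 1.55–1.75 | 17–21% | 32–38% | 3.0–4.5% |

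If AHCL halved the rate (35 per arm), the chance of at least one empty arm would be 93%, 79% and 52% at control rates of 5, 10 and 20.

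These figures count admissions over the full three months. The Visit 6 list in section 4.2 asks for "Hospital admissions since Visit 5 for Control arm / Visit 4d for Intervention arm". If only that window were counted in the control arm (about 2 to 4 weeks), the chance of no control admissions at 10 per 100 child-years would rise from 42% to 76–87% with 35 children.

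**What the specified model does** (35 per arm, 91 days each).

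- Poisson, 0 v 2: log rate ratio −11.4 (SE 127) after 10 iterations, −26.4 (SE 2.3 × 10⁵) after 25, −34.2 (SE 1.0 × 10⁷) after 50. The Wald p value goes to 1.
- Poisson, 0 v 0: the fit fails.
- Negative binomial, 0 v 3: log rate ratio −11.2 (SE 160), although the routine reported convergence.
- Poisson, 1 v 2: rate ratio 0.50 (SE of the log 1.22), an ordinary fit. The empty arm is the cause of the failure.

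**Tests when all k events fall in one arm, equal exposure.** Likelihood-ratio chi-square = 2k ln 2 on 1 df; exact two-sided p = 2 × 0.5^k; mid-P = 0.5^k.

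| Split | Wald p | Likelihood-ratio p | Exact p | Mid-P |
|---|---|---|---|---|
| 3 v 0 | about 1 | 0.041 | 0.25 | 0.125 |
| 5 v 0 | about 1 | 0.008 | 0.063 | 0.031 |

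Given three events in all and equal true rates, all three fall in the same arm with probability 2 × 0.5³ = 25%. The likelihood-ratio test at nominal 5% therefore rejects 25% of the time in that situation.

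**What exact methods give.** For 0 v 3 the exact conditional 95% interval for the rate ratio is 0 to 2.4, and for 0 v 2 it is 0 to 5.3. Zero events in 8.75 child-years has an exact 95% upper limit of −ln(0.025)/8.75 = 3.69/8.75 = 0.42, or 42 per 100 child-years.

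**The case against.** The strongest reply is that section 9.1 names a standard model with sensible offsets and an overdispersion rule, and that handling an empty cell belongs in the SAP. An unseen SAP may well add an exact method. But the protocol does name a method for these counts, and that method fails on foreseeable data. Section 9.4 requires deviations from the statistical plan to be reported to the ethics and governance committees and the DSMB, so settling it in 9.1 is easier than switching later.

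It is also fair that admissions sit among the health-economic outcomes, where zero is a valid input to a cost-effectiveness ratio, and that secondary outcomes are exploratory. That lowers the severity.

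Four stronger readings are tempting, and the protocol does not support them:

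- *Severe hypoglycaemia and DKA are committed to this model.* Section 4.1 names neither for the RCT; 4(b) says only hypoglycaemic events. Both are collected at Visit 6, so the routing is an inference. Severe hypoglycaemia is the primary safety outcome in 4.9, with its own sequential monitoring by the DSMB, and an algorithm-related severe DKA triggers a DSMB review.
- *The protocol's own evidence predicts an empty arm.* Section 2 reports that a pivotal AHCL trial in 157 people aged 14–75 "demonstrated no occurrences of severe adverse events", and no serious adverse events in 16 children under 7. All were closed-loop users, so nothing follows for the control arm. The 16 children contribute 16 × 6.3/12 = 8.4 child-years, which is compatible with up to 3.00/8.4 = 0.36 events per child-year (one-sided 95%). At that rate, with 35 per arm, the chance of an empty arm is only about 9%.
- *The likelihood-ratio p value is always far too small.* Averaged over all outcomes, the test's size at the three assumed rates is 1.0–1.3%, 4.1–4.9% and 9.0–9.5%. It is inflated overall only at the highest rate. The problem is conditional on the few events actually seen. At 5 v 0, mid-P is also below 0.05.
- *Zero events would be taken as proof of safety.* Nothing in the protocol says so. Also, if only the AHCL arm is empty, the rate ratio itself is 0 and a profile-likelihood upper limit exists (0.90 for 0 v 3). What is missing is a finite log ratio and a usable Wald interval.

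**Conclusion.** The point holds for diabetes-related admissions. The specified model gives no finite log rate ratio or usable Wald interval when an arm is empty, gives nothing when both are, and its only fallback does not help. The chance of at least one empty arm runs from about one in three to nine in ten across the assumed range. That range rests on assumed equal rates, independent Poisson events and full three-month counting; a rate well above 20 per 100 child-years would make the problem uncommon. Severity is low, because the outcome is exploratory and no primary conclusion depends on it.

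**What to change.** In section 9.1, take admissions out of the Poisson/negative binomial rule. Do the same for severe hypoglycaemia and DKA if they are to be compared between arms as secondary counts, separately from the DSMB's sequential monitoring. For these outcomes report:

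- the number of events and of children affected per arm;
- each arm's rate with an exact Poisson 95% interval, including the upper limit when there are no events;
- an exact conditional (mid-P) rate-ratio test and interval, with child-time as exposure over the same window in which events are counted.

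Keep Poisson or negative binomial regression for frequent counts, such as CGM-derived events. This takes one or two sentences and no new data, and leaves the primary analysis unchanged. The price is no covariate adjustment for these events, and visibly wide intervals.
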